### ***Current proposal***

There is a difference in the systemic response to periodontal treatment using hand instruments, compared to ultrasonic instrumentation.

#### **1.1.1. ADDITIONAL ANALYSES TO THOSE SPECIFIED IN THE STUDY PROPOSAL**

Nil

#### **Research questions**

Is there a difference in the systemic response to periodontal treatment using either hand instruments, as compared with periodontal treatment using ultrasonic instruments.

#### **Software**

All statistical analyses will be carried out with Stata v 16 (or PRISM) or higher versions of these programs.

#### **5.2 Primary efficacy analysis**

There is no test intervention therefore no efficacy analysis.

#### **5.3 Secondary efficacy analysis**

*n/a*

#### **5.4 Safety analysis**

The safety data (adverse events) – both numbers of subjects and events – will be summarised.

Adverse Event (AE) – any unfavourable and unintended sign, symptom or disease temporally associated with participation in the research project.

Serious Adverse Event (SAE) - An untoward occurrence that:

- a. results in death
- b. is life threatening
- c. requires hospitalisation or prolongation of existing hospitalisation

- d. results in persistent or significant disability or incapacity
- e. consists of a congenital anomaly or birth defect
- f. is otherwise considered medically significant by the investigator

Any SAE occurring to a research participant will be reported to the main REC) where in the opinion of the Chief Investigator (CI), the event was:

- “Related” – that is, it resulted from administration of any of the research procedures, and
- “Unexpected” – that is, the type of event is not listed in the protocol as an expected occurrence.

Reports of related and unexpected SAEs will be submitted to the REC within 15 days of CI becoming aware of the event, using the ‘report of serious adverse event form’ for non-CTIMPs published on the National Research Ethics Service (NRES) website.

### **5.5 Software for statistical analysis**

All statistical analyses will be carried out with Stata v 16 (or PRISM) or higher versions of these programs

### **5.6 Management and delivery**

[name] and colleagues will manage and analyse study data.

## **6. STUDY CLOSURE / DEFINITION OF END OF TRIAL**

The study will end when the CI deems that one or more of the following situations applies:

OR

- i. The planned sample size has been achieved;
- ii. There is insufficient funding to support further recruitment, and no reasonable prospect of additional support being obtained;
- iii. Recruitment is so poor that completion of the study cannot reasonably be anticipated.

## **7. DATA HANDLING**

### **7.1 Case Report Forms**

Patient data will be collected at the time of sample collection and recorded on the CRF. At the time of sample collection, each sample will be assigned a code, recorded on the CRF. All data associated with analysis of the samples will be collected and stored linked only to the code. The data linking the patient code with the patient data will be stored securely on University of Glasgow Computers, using password protected file encryption. Hard copies will be stored in a locked file at the University of Glasgow Dental School. The data recording sample analysis will include only the patient code and will also be stored on University of Glasgow Computers but will NOT be encrypted. Hard copies of this data will be stored in laboratory record books, kept at the University of Glasgow Dental School. Samples will be stored appropriate to the type of sample, within facilities at the University of Glasgow, with a detailed description of the sample location, use(s) and ultimately disposal, documented in a sample log record. Any data changes will be recorded in order to maintain a complete audit trail (reason for change, date change made, who made change).

### **7.2 Record Retention**

To enable evaluations and/or audits from regulatory authorities, the investigator agrees to keep records, including the identity of all participating subjects (sufficient information to link records), all original signed informed consent forms, serious adverse event reports, source documents, and detailed records of treatment disposition in accordance with ICH GCP, local regulations, or as specified in the Clinical Study Agreement, whichever is longer. Data will be retained by the research team for 15 years.

## **8. TRIAL MANAGEMENT**

### **8.1 Routine management of trial: Trial Management Group**

The study will be coordinated from The University of Glasgow Dental Hospital, by the Trial Management Group. The Trial Management Group will include the CI, statistician, research nurse, and laboratory investigators involved in use of clinical samples. The group will monitor all aspects of the conduct and progress of the study, ensure that the protocol is adhered to and take appropriate action to safeguard participants and the quality of the study itself.

See Data Security Protocol.

## **9. STUDY AUDIT**

Study site-set up visit and site file will be provided once the study has received R & D approval. Study audit visits will be conducted according to NHS Greater Glasgow and Clyde audit processes. Additional visits may be undertaken if required. Investigators and site staff will be notified in advance of any audit visits.

## **10. PROTOCOL AMENDMENTS**

Any change in the study protocol will require an amendment. Any proposed protocol amendments will be initiated by the CI following discussion with the Sponsor and amendment forms will be submitted to the REC and R&D. The CI will liaise with Sponsor to determine whether an amendment is non-substantial or substantial. All amended versions of the protocol will be signed by the CI and Sponsor representative. Before the amended protocol can be implemented favourable opinion/approval must be sought from the original reviewing REC and R&D office.

## **11. ETHICAL CONSIDERATIONS**

### **11.1 Ethical conduct of the study**

The study will be carried out in accordance with the World Medical Association Declaration of Helsinki (1964) and its revisions (Tokyo [1975], Venice [1983], Hong Kong [1989], South Africa [1996] and Edinburgh [2000]).

Favourable ethical opinion will be sought from an appropriate REC before patients are entered into this research study. Patients will only be allowed to enter the study once either they have provided written informed consent.

The CI will be responsible for updating the REC of any new information related to the study.

### **11.2 Informed consent**

Written informed consent should be obtained from each trial participant. Only patients able to consent for themselves will be included in the study. The Consultant or his/her representative, or the Research Nurse will explain the exact nature of the study in writing, provision of patient information sheet, and verbally. This will include the known side-effects that may be experienced, and the risks of participating in this clinical trial. Trial participants will be informed that they are free to withdraw their consent from the study or study treatment at any time, and it will be emphasised to participants that their decision to participate in the study does NOT influence the treatment they will receive in any way.

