#### **Screening visit: New patient assessment**

Patients are referred then appointed on a new patient consultant clinic at which a clinical history and clinical examination are completed by the consultant or his/her staff. A treatment plan is then agreed with the patient. If this treatment plan includes periodontal treatment at Glasgow Dental Hospital and the patient is eligible to take part, then the patient will be provided with written and verbal information about the study. The patient will be asked to give an initial indication as to whether they would consider taking part – with emphasis that they should take time to consider the PIL and will have the opportunity to ask further questions, and that their treatment remains unaltered irrespective of their participation. If the patient indicates they would consider participation in the study, they will be appointed jointly to the GDHCRF and the hygienist / registrar (baseline visit).

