#### **Baseline visit:**

If the patients initially said YES to participating in the study at the screening visit, at this visit, prior to the start of treatment the patient will be asked if they have further considered participation in the study. If yes, consent for sample collection will be sought and samples will be collected by the GDHCRF research nurse and/or dentist/hygienist (the hygienist or dentist will generally only collect plaque samples as s/he will be removing the plaque anyway). This visit includes FMPS & FMBS & Periodontal charting, blood pressure recording, BMI recording and sample collection of GCF, plaque & blood). This visit is also for initial periodontal charting and initial treatment. This visit includes detailed tooth and gum home care instructions and a superficial scaling of the teeth. This is usually carried out by a staff or research hygienist, but may also be undertaken by training grade staff under the supervision of a consultant.

gingival indices will be taken. The patient will then be randomised to full mouth non-surgical periodontal treatment using either hand scalers or ultrasonic instrumentation. Appointments will be made for patient to attend for treatment visits, Day1, Day 7 and Day 90 visits with time in the GDHCRF for sample collection / blood pressure, BMI and periodontal charting where applicable.

**Treatment visits** - full mouth non-surgical periodontal treatment will be carried out within a 24hr period (+/- 18hr) either using hand instrumentation or ultrasonic instrumentation as per randomization. At the last treatment visit the clinician will verbally enquire whether the patient is happy to continue participation in the study. If yes - then the patient should attend Day 1 (24hrs later (+/- 18hrs) with time in the GDHCRF for sample collection / blood pressure recording.

**Day 1** - 24 hours (+/-18hrs) after treatment completed, further samples (GCF/Plaque/blood) and blood pressure recording will be performed. At this visit the clinician will verbally enquire whether the patient is happy to continue participation in the study. If yes - then the patient should attend Day 7 (+/- 1 day) with time in the GDHCRF for sample collection / blood pressure recording, & review of ohi

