## **5. STATISTICS AND DATA ANALYSIS**

### **5.1 Statistical analysis plan**

Randomized controlled trial to investigate the difference in systemic response to periodontal therapy, using two different treatment modalities – hand instrumentation and ultrasonic instrumentation. Patients will receive one of two interventions – hand instrumentation or ultrasonic instrumentation, as treatment for their periodontal disease. These two interventions will be compared through the following outcomes.

The primary outcome is that of systemic inflammatory response, measured through serum CRP. A variety of secondary outcomes will also be investigated, including clinical outcomes related to periodontal disease; microbiome analysis; inflammation and immune response analysis.

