#### ***Stratification and Randomization Methods***

Our target population is that of patients suffering from periodontal disease.

Randomization to either intervention (hand instrumentation or ultrasonic instrumentation) will be performed using a computerised random number generator (using permuted blocks of size 4 and 6). Patients will be stratified according to smoking status prior to randomization.

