#### ***Allocation Concealment***

Patients will be allocated to each arm of the study by a member of the research team not involved with the clinical delivery of the experimental interventions. Upon attending their treatment appointment, an opaque envelope will contain the allocated intervention arm for the patient. This will be opened immediately before treatment is commenced.

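### Staff are told to assure patients that taking part does not influence their treatment, yet randomisation sets every participant's scaling instrument

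*Combined protocol and SAP*

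**What the plan says.** Two places tell patients that the study leaves their treatment alone.

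- Section 4.1, Screening visit: when the patient is asked for a first indication of interest, staff are to stress that "their treatment remains unaltered irrespective of their participation".
- Section 11.2, Informed consent: staff are to emphasise to participants that "their decision to participate in the study does NOT influence the treatment they will receive in any way". The capitals are the protocol's own.

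Other places describe a randomised trial of treatment.

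- Section 4.1, Baseline visit: "The patient will then be randomised to full mouth non-surgical periodontal treatment using either hand scalers or ultrasonic instrumentation".
- Section 5.1: "Patients will receive one of two interventions", and the allocation comes from a "computerised random number generator (using permuted blocks of size 4 and 6"), stratified by smoking status. The Synopsis and the randomisation paragraph in section 3.3 say the same.
- Section 5.1, Allocation Concealment: the allocation is in an opaque envelope that the patient's treatment team sees only at the treatment appointment. "This will be opened immediately before treatment is commenced".

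On the scope of consent, the baseline visit text says that "consent for sample collection will be sought". It does not mention randomisation at that point. The Synopsis and section 3.4 speak more broadly of consent to take part. Section 3.4 also contains an accurate assurance: participation is voluntary, and leaving does not harm the patient's care.

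**The concern.** Wording of this kind suits an observational study in which patients give samples while their care goes on as it would have done. This is not that study. The instrument used on each participant is the experimental factor, and the trial assigns it.

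The protocol itself treats the choice of instrument as important. Its hypothesis (section 1.4) is that the two instruments produce different systemic responses. Its rationale (section 1.2) suggests that their immediate effects on patients may differ. Patient preference between them is among the secondary objectives (Synopsis and section 2). A patient deciding whether to join could reasonably want to know that the study will decide which one is used.

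What is at stake is the accuracy of what participants are told before they agree. Staff who follow the protocol to the letter must stress something that the design makes untrue, and could be contradicting the leaflet as they do so.

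**Working it through.** No arithmetic applies. The check is whether the assurance can be true of someone who joins.

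| Question | Assurance (4.1 Screening visit; 11.2) | Design (Synopsis; 3.3; 4.1 Baseline visit; 5.1) |
|---|---|---|
| Does joining change how treatment is decided? | No, not in any respect | Yes: a randomisation schedule sets the instrument |
| Who is covered? | Patients invited to join, and participants | Every participant |
| When is the instrument known? | Not addressed | When the envelope is opened, just before treatment |

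1. *A patient who declines.* The study assigns nothing and the patient is treated as usual. The assurance is true.

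2. *A patient who joins.* The randomisation schedule sets the instrument. For the assurance to be true, treatment would have to be the same whether or not the patient joined. The documents do not say how the instrument is chosen in usual care. I assume that it is not drawn from a randomisation schedule. On that assumption the way treatment is decided changes for everyone who joins, and the instrument itself may change.

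3. *Can a narrower meaning rescue the text?* One could read it as saying only that refusal carries no penalty. Section 3.4 already says that leaving carries none, and says it accurately. Section 11.2 goes further: it concerns the decision to participate, addresses participants, and allows no exception. The same sentence lets participants withdraw from study treatment, so it acknowledges that the study supplies a treatment while denying that it influences treatment.

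4. *Does the described scope of consent cure it?* Taken alone, the baseline visit text mentions consent only for samples, and randomisation follows at that visit. The Synopsis and section 3.4 refer to consent to take part, and the Schedule of Assessments lists written consent and randomisation as separate baseline items. Read together, these passages suggest that consent is meant to cover the whole study. None of them says that it covers random allocation of treatment.

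The two assurances and the design cannot both stand as written.

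**The case against.** The strongest reply is that the sentence is one part of a longer consent process. Section 11.2 also requires staff to explain the full nature of the study, verbally and in writing, together with the risks of taking part in a clinical trial. The leaflet and the consent form, which may describe randomisation clearly, are not in the text supplied. This part of the reply stands. A reader might infer that consent in this trial is invalid, or that patients are not told about randomisation. The documents do not support either inference. They show one required statement that is untrue, next to a requirement for full disclosure.

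A second reply is that both arms are standard care (Synopsis) and that the study stages are described as part of the normal pathway (Study Flow Chart legend). This limits the consequence, because no participant receives a non-standard instrument. It does not make the statement true: that either instrument might be used in normal care is different from chance choosing between them.

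A third concerns tolerance. The Synopsis refers to patients who cannot tolerate ultrasonic instrumentation even with local anaesthesia. That is an exclusion criterion there, so it is not evidence that such patients would be enrolled unaware. The full list in section 3.3 omits the criterion. That is a separate inconsistency, which must be reconciled.

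Finally, a reader might infer that the wording will cause patients to drop out when the envelope is opened, with losses that differ by arm. Such refusals are possible, but the cause is the late reveal, which protects allocation concealment, together with the freedom to withdraw. Both would remain under corrected wording. The documents give no refusal rate, and the sample size section already allows for 20% loss. Clearer wording might move some objections to before randomisation, but nothing in the documents says how many.

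**Conclusion.** The contradiction holds. Sections 4.1 (Screening visit) and 11.2 instruct staff to give an assurance that is untrue for anyone who joins, because randomisation sets the instrument. It is an error in the text, not merely missing detail, and it bears on participant protection. It should be fixed.

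The instruction applies to every participant, 42 by the recruitment target. No numerical effect on the trial's results can be derived. The sample size, the power, the endpoints and the analysis are unaffected.

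The conclusion rests on the protocol wording and on one assumption, that usual care does not choose the instrument by a randomisation schedule. It makes no claim about what patients have actually been told, which depends on the unseen leaflet and consent form. It also makes no claim about dropout.

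**What to change.** 1. In section 4.1 (Screening visit) and section 11.2, replace the assurance with wording in line with section 3.4, for example: *Declining or withdrawing will not affect the patient's care. Patients who take part will have their instrument, hand or ultrasonic, chosen at random and revealed at the treatment visit.*
2. In section 4.1 (Baseline visit), state that consent covers taking part in the randomised study, including random allocation of the instrument, as well as sample collection.
3. Check the participant leaflet and the consent form against this wording, and amend them if they differ.

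The change is to wording only. Under section 10 it is a protocol amendment that needs ethics committee and R&D approval before use. A few patients with a strong preference for one instrument may decline once the position is clear, but they would do so before randomisation, so the comparison between arms is not disturbed.

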## **12. INSURANCE AND INDEMNITY**

The sponsor will be liable for negligent harm caused by the design of the trial. NHS indemnity is provided under the Clinical Negligence and Other Risks Indemnity Scheme (CNORIS).?

The NHS has a duty of care to patients treated, whether or not the patient is taking part in a clinical trial, and the NHS remains liable for clinical negligence and other negligent harm to patients under its duty of care.

### **13. FUNDING**

University of Glasgow Studentship

#### **14. ANNUAL REPORTS**

Reports to the sponsor will be coordinated by the university. Annual reports will be submitted to the REC and sponsor with the first submitted one year after the date that all trial related approvals are in place.

## **15. DISSEMINATION OF FINDINGS**

Findings will be presented locally at group meetings, seminars at Glasgow Dental School and at the Institute of Infection, Immunity and Inflammation. In addition, findings will be presented at national and international meetings and submitted to peer review journals. Public engagement in research is important to the investigators and funders. Therefore, outreach activities such as 'meet the expert' at Glasgow Science Centre will include findings from these studies and significant findings of broader interest will be promoted with advice and support from the University of Glasgow press office to publicise any key developments and to engage with a wider audience.

